9.1 Monitoring of study centers

The research centers participating in the study will be monitored. For each center, at least one start visit and one closing visit must be carried out, which does not exclude the carrying out of one or more follow-up visits between these two mandatory visits.

The basal visit must be carried out before the inclusion of the first participant in that center; In it, the monitor will verify that the material to be used during the study has been received and that the personnel who will participate in the study activities have been trained on the study, as well as verify that the regulatory requirements and applicable standard operating procedures are met.

At the follow-up visit, the monitor will conduct a review of the study documents to confirm that: the applicable research protocol and standard operating procedures are being followed, data completion is complete and timely, and AE reports are being conducted appropriately. At each visit, the monitor will discuss the findings with the researcher and define the actions to be taken.

The final visit will take place at the end of the study, once the last participant in the last site has been discharged from follow-up. During this visit, the monitor will verify that the site has all the necessary documents to archive, that all biological samples have been sent for analysis, that all study drug (used and unused) has been recovered and sent to the sponsor, and that all unused material has been recovered.

Details on monitoring are set out in the corresponding plan.

9.2 Audit and quality control

To ensure compliance with GCPs and all applicable regulatory requirements, Laboratorios Sophia, S.A. de C.V. may conduct quality assurance audits. Regulatory agencies could also conduct a regulatory inspection of this study.

Details about the audit process are set out separately in an Audit Plan.

9.3 Pre-study audit

Study sites included in the study will be subject to a pre-site feasibility visit, where they will be verified to meet the minimum requirements indicated by the sponsor.

9.4 Audit during the conduct of the study

They may take place at any time before, during, or after the conclusion of the study. If any audit or inspection is conducted, the investigator and the institution shall agree to allow the auditor/inspector direct access to all relevant documents, and shall allocate their time and that of their staff to the auditor/inspector to discuss the findings and any pertinent problems. In the event that the audit has not been scheduled by the sponsor, the facility must notify Laboratorios Sophia, S.A. de C.V. immediately.

10. Statistical analysis

10.1 Data analysis

10.1.1 Statistical analysis

The statistical analysis will be carried out by personnel of Laboratorios Sophia, S.A. de C.V. The statistical package SPSS version 19.0 for Windows (IBM Corporation, Armonk, NY, USA) will be used.

Although the study design is open-label, the personnel designated for the statistical management of the data will be blinded to the intervention groups to avoid possible interpretation biases. Coding will be performed using consecutive numbers for each intervention group.

The data will be collected and sorted in an Excel spreadsheet (Microsoft® Office). The data will then be exported to the SPSS package platform. The variables will be categorized according to their nature (see Table 3).

10.1.2 Data interpretation

The Kolmogorov-Smirnov and Shapiro Wilk tests will be performed, as appropriate, to determine if the distribution is normal in the results obtained in each study group [59].

The results of the continuous quantitative variables will be presented in measures of central tendency: mean, standard deviation and/or range.

- Intragroup analysis: Differences within groups will be analyzed using the one-way ANOVA or the Student's t-test when applicable.
- Inter-group analysis: For equal variances, Tukey's post-hoc test will be used, otherwise Dunnett's statistic will be used. Student's t-test will be used when applicable.

The level of difference to consider significance will be an alpha (α) of 0.05 or less. A 95% confidence interval (95% CI) will be considered for non-inferiority criteria [60].

The result of the nominal and ordinal qualitative variables will be presented in frequencies, proportions and percentages.

The statistical analysis to identify significant differences in the qualitative variables will be carried out by creating 2x2 contingency tables and will be carried out as follows:

- Intra-group difference: McNemar test. This is applied to 2x2 contingency tables with a dichotomous feature, with pairs of paired subjects, to determine if the marginal frequencies of row and column are equal (marginal homogeneity).
- Difference between groups: Pearson's Chi-square test (X^2) or Fisher's exact test at expected values less than 5.

The level of difference to consider significance will be an alpha (α) of 0.05 or less.

For the reporting of AEs, all eyes of those participants who were randomly assigned to an intervention group after the baseline visit will be considered. The results will be expressed in number of subjects.

The final report of the results will be shown in tables or graphs, as appropriate.

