Safety primary outcome variable:

- Incidence of AEs (ET: days 15 and 31).

[figure not shown]
Safety Secondary Outcome Variable:

- Changes in the BCVA (ET: day 15 and 31).
- Changes in intraocular pressure (IOP) (ET: day 15 and 31).

Statistical methodology

The Kolmogorov-Smirnov and Shapiro Wilk tests will be performed, as appropriate, to know if the distribution presents normality in the results obtained in each study group. The data will be expressed with measures of central tendency: mean and standard deviation for the quantitative variables. Qualitative variables will be presented in frequencies and percentages. The statistical analysis will be performed by means of the Analysis of Variance Test (ANOVA) for the quantitative variables for the difference between the groups. The difference between the qualitative variables will be analyzed by means of X² (Chi-square) or Fisher's exact. A 95% CI will be considered for the non-inferiority criteria based on the objectives of the study, an alpha (α) will be considered significant ≤ 0.05

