3.4 Hypotheses

H₀: Multi-dose Lagricel® Ofteno decreases the OSDI test score by 20% or more at the end of the study in at least 1 of the proposed dosages.

H₁: Multi-dose Lagricel® Ofteno does not decrease the OSDI test score by 20% at the end of the study in at least 1 of the proposed dosages.

4. Study design

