7.4 Outcome variables

7.4.1 Primary outcome of efficacy

- OSDI test score (ET: day 31).

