7.4.5.3 Corneal and conjunctival staining with fluorescein

A drop of topical anesthetic will be instilled in the bottom of the conjunctival sac, then a second drop will be applied to the tip of the fluorescein strip, allowing it to sit on the strip for 5 seconds to elute the dye, shaking off the excess at the end. A small contact of the strip is made with the conjunctiva at the fundus of the temporal sac, while the patient looks upwards, without damaging the conjunctiva. It will be graded according to the Oxford scale (See: 16.2). [50]

The PI will record in the file and the eCRF the grade awarded for fluorescein staining of DO and OS, respectively.

Management as AE: corneal stains that are equal to or greater than grade III will be considered as AEs.

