10.1.4 Deviations from the statistical plan

According to the calculation of the sample size to meet the primary objective of the study, 141 evaluable subjects (47 subjects per dosage) are required. If this number is not met due to a loss of subjects greater than 20% contemplated in this protocol (loss of follow-up or withdrawal of ICF), in order to balance the treatment groups, the sponsor may replace these subjects.

The results obtained from the substituted subjects will continue to be used for safety analysis and will be part of the *Intention To Treat* population (ITT).

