10.2.2 Justification of the sample size calculation

The sample size calculation was made based on the study by Pinto-Fraga et al. (2017), where they evaluated the safety and efficacy of an artificial tear of 0.2% hyaluronic acid (HA) versus SS (saline, 0.9% NaCl) in patients with mild dry eye (OSD) after one month of treatment. Subjects treated with HA had a decrease of -19.66% with respect to their initial mean value, while in subjects treated with SS there was a significant increase in the final OSDI score of 12.47%, $p < 0.05$ compared to the initial [61].

For the calculation, a decrease in the OSDI score of 20% was considered for the formulation proposed in this protocol (Multi-dose Lagricel® Ofteno) with respect to its initial mean value in subjects with mild to moderate DED.

The sample size was calculated using the equation for two proportions [62], considering a power of 80% (β), a significance level of 0.05 (α) and a non-inferiority margin (δ) of 10%, based on the following working hypotheses:

$$H_0: P_A - P_B \leq \delta$$

$$H_1: P_A - P_B > \delta$$

Where, δ is the margin of non-inferiority and the ratio between the sample size of the two groups is:

$$k = \frac{n_A}{n_B}$$

The calculation to estimate the sample size and power was done using an online tool and following the equations [63]:

$$n_A = kn_B, n_B = \left(\frac{P_A(1 - P_A)}{k} + P_B(1 - P_B) \right) \left(\frac{z_{1-\alpha} + z_{B-\beta}}{P_A - P_B - \delta} \right)^2$$
$$1 - \beta = \Phi(z - z_{1-\alpha}) + \phi(-z - z_{1-\alpha}), z = \frac{P_A - P_B - \delta}{\sqrt{\frac{P_A(1 - P_A)}{n_A} + \frac{P_B(1 - P_B)}{n_B}}}$$

Where:

- $(k = \frac{n_A}{n_B})$ is the allocation ratio,
- (Φ) is the standard normal distribution function,
- (α) is the Type I error,
- (β) is the Type II error, meaning that $(1 - \beta)$ is the power, and
- (δ) is the test margin.

According to the previous calculation, the result is 39 subjects, this calculation was increased by 20% considering possible losses (8 subjects). The total suggested sample size is 141 subjects (47 subjects per treatment dosage), who will contribute OU to the study.

11. Ethical considerations

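### The between-dosage comparison of day-31 OSDI makes no use of the baseline OSDI collected on every subject; adjusting for it would tighten the estimates at no cost in data

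*Combined protocol and SAP*

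**What the plan says.** The between-dosage test is described in three places.

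- The synopsis, under statistical methodology, plans the "Analysis of Variance Test (ANOVA) for the quantitative variables for the difference between the groups".
- Table 3 (section 7.4.5) gives ANOVA, or Student's t-test when applicable, for OSDI, measured at the basal and final visits.
- Section 10.1.2 adds the pairwise step: "Inter-group analysis: For equal variances, Tukey's post-hoc test will be used, otherwise Dunnett's statistic will be used". Student's t-test is again allowed when applicable.

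None of these names a covariate, and ANCOVA appears nowhere in the document.

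On the response, section 7.4.1 lists the primary outcome as the OSDI score at day 31, and Table 3 gives its unit as a score. Section 7.4.3 words its outcomes as changes, chemosis excepted. The hypothesis in section 3.4, however, is that the product "decreases the OSDI test score by 20% or more at the end of the study" in at least one dosage, and section 10.2.2 plans on a 20% fall "with respect to its initial mean value in subjects with mild to moderate DED".

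For comparisons within an arm, section 10.1.2 says: "Differences within groups will be analyzed using the one-way ANOVA or the Student's t-test when applicable". Pairing is mentioned only for McNemar's test on the qualitative variables.

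**The concern.** Baseline OSDI is recorded before treatment, on the same scale as the outcome, and no subject can be enrolled without it because entry requires a score from 13 to 32 (section 5.1.1). A plain ANOVA of day-31 scores leaves the variation that baseline explains in the error term and leaves chance baseline imbalance in the dosage differences. All three arms receive the same product, and sections 2.5.1 and 4.2 give finding the ideal dosage as a purpose, so the differences of interest may be small and precision matters.

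The 20% fall in sections 3.4 and 10.2.2 also leaves some doubt whether the raw score or the change is to be tested, and the two differ in precision.

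The intragroup line raises a related, smaller question. One-way ANOVA in its standard form treats visits as independent groups, and so discards the pairing of each subject with him- or herself.

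**Working it through.** **Inputs.** Section 10.1.4 states that "141 evaluable subjects (47 subjects per dosage) are required". Section 10.2.2 reaches 47 as 39 × 1.2 = 46.8, rounded up, and 3 × 47 = 141; this reproduces. The 39 itself needs a second proportion that the section does not state, and nothing below depends on it.

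The documents give no OSDI SD and no baseline to day-31 correlation r. Assumptions:

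- SD 5.5, from a uniform spread over the entry range: (32 − 13)/√12 = 5.48.
- SD 8 as a wider case, because day-31 scores are not bounded by the entry criterion.
- r from 0.2 to 0.6.

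**Raw score against ANCOVA.** Residual variance relative to raw scores is 1 − r²: 0.96 at r = 0.2 and 0.64 at r = 0.6, a cut of 4% to 36%. The 95% CI half-width for two dosages, before any Tukey adjustment, is t × SD × √(relative variance) × √(2/47). Here √(2/47) = 0.2063, and t = 1.977 on 138 df (137 for ANCOVA).

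| Day-31 SD | Raw score | ANCOVA, r = 0.2 | ANCOVA, r = 0.6 |
|---|---|---|---|
| 5.5 | 2.24 | 2.20 | 1.79 |
| 8 | 3.26 | 3.20 | 2.61 |

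With 39 per arm every entry is about 10% wider (√(47/39) = 1.10); the variance ratios do not move.

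**Change score against ANCOVA.** The variance of a change is SD₀² + SD₁² − 2r·SD₀·SD₁, so this comparison depends on both SDs.

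- *Equal SDs.* Relative to raw, the change score has variance 2(1 − r): 1.6 at r = 0.2 and 0.8 at r = 0.6. The ANCOVA to change ratio is (1 + r)/2 = 0.60 and 0.80, a cut of 40% to 20%. Change and raw scores are equally precise at r = 0.5.
- *SD 5.5 at baseline, 8 at day 31.* The change variance is 94.25 − 88r: 76.65 at r = 0.2 and 41.45 at r = 0.6, with half-widths 3.57 and 2.63. The ANCOVA variance is 64(1 − r²): 61.44 and 40.96, with half-widths 3.20 and 2.61. The cut is 20% at r = 0.2 and about 1% at r = 0.6. Change and raw scores are equally precise at r = 30.25/88 = 0.34.

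**Within an arm.** A 20% fall from the middle of the entry range is 0.20 × 22.5 = 4.5 points. (Taking the fall from either end of the range would require every subject to share one baseline score.) With n = 47, r = 0.5 and equal SDs, the SD of the change equals the single-visit SD.

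- *SD 8.* The paired standard error is 8/√47 = 1.167, the noncentrality 4.5/1.167 = 3.86, and the power about 97%. An unpaired test uses 8 × √(2/47) = 1.650 as its standard error; its power by simulation is about 85%.
- *SD 5.5.* Power exceeds 99% for both.

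**The case against.** The strongest reply is that the plan's comparison is valid and that its response is reasonably clear. Section 7.4.1 lists a day-31 score, the secondary outcomes are worded as changes by contrast, and Table 3 puts ANOVA on the same line as the score. This largely stands. The natural reading is ANOVA of the day-31 score; the 20% wording leaves residual doubt, not an undefined endpoint. Under that reading the unused baseline remains.

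The gain may also be small. At r = 0.2 the half-width shrinks by only about 2%, and restricting entry to 13–32 tends to lower r. That stands too: the size is uncertain, but the cost is one degree of freedom.

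On the intragroup line, pairing may well be intended, since McNemar's test is the paired counterpart for the qualitative variables and a paired t-test is not excluded. An unpaired test would also err on the conservative side.

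A reader might infer three stronger points that the documents do not support.

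- *That omitting baseline biases the dosage comparison.* Allocation is randomized, so it costs precision, not validity.
- *That change scores are less precise than raw scores whenever r is below 0.5.* This holds only if the two SDs are equal, and the documents give neither.
- *That false positives are inflated because both eyes are counted.* Section 7.4.5.3 does record "the grade awarded for fluorescein staining of DO and OS, respectively", but no section says that eyes will be analysed as independent observations, and OSDI is one score per subject.

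**Conclusion.** The point holds as an improvement in efficiency, not as a flaw that invalidates the primary comparison. Baseline adjustment narrows the 95% CI for a dosage difference by about 2% at r = 0.2 and about 20% at r = 0.6 relative to raw day-31 scores. Against change scores the gain runs from substantial to almost nil, depending on r and on the ratio of the two SDs. All of this rests on assumed SDs and correlations. What does not depend on them is that ANCOVA is, apart from one degree of freedom, at least as precise as either alternative under the usual linear model, so choosing it removes the need to guess r in advance.

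The intragroup wording is a secondary correction. If it were applied unpaired, power for a 4.5-point fall would be about 85% instead of 97% at SD 8, with practically no loss at SD 5.5.

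**What to change.** In section 10.1.2, Table 3 and the synopsis, state that day-31 OSDI is analysed by ANCOVA with dosage as factor and baseline OSDI as covariate, and that adjusted dosage differences are reported with 95% CIs. This also settles which response is tested.

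ANCOVA of dosage differences does not address the 20% fall in section 3.4. Add a within-arm estimate of the fall from baseline, with its CI, for each dosage.

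In the intragroup line, replace one-way ANOVA with a paired t-test for OSDI (two visits) and a repeated-measures model for quantitative variables measured at three visits, such as TFRT. Say explicitly that the t-test is paired.

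The cost is SAP wording and slightly more analysis work. No new data, visits or subjects are needed.

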4.2 Justification of the study design

The design of the study (clinical trial) is considered the highest standard of data quality when seeking to explore the effect of an intervention. The drug development phase (phase II) corresponds to the objective of the study, which is to evaluate efficacy and ideal dosage. The presence of parallel groups allows comparison between intervention groups on outcome variables. Due to the nature of the design, blinding was not considered for this study.

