7.4.5 Definition of variables, methods and scales to be used for measurement

Variable	Type of variable	Unit (symbol)	Method of measurement	Normal value	Evaluation time	Test statistics
Primary outcome of efficacy						
OSDI	Quantitative discrete	Score	Questionnaire	< 13	BV and FV	ANOVA Student's t test*
Secondary outcome of efficacy						
TFRT with fluorescein	Quantitative continuous	Second(s)	Direct observation with slit lamp and cobalt blue filter	> 10s	BV, V1 and FV	ANOVA Student's t test*
Corneal and conjunctival staining with lissamine green	Categorical ordinal	Degrees	Direct observation with slit lamp, evaluated with Oxford's scale	0	BV, V1 and FV	Pearson's χ^2 or Fisher's exact test. McNemar's test*
Corneal and conjunctival staining with fluorescein	Categorical ordinal	Degrees	Direct observation with slit lamp, evaluated with Oxford's scale	0	BV, V1 and FV	Pearson's χ^2 or Fisher's exact test. McNemar's test*
Conjunctival hyperemia	Categorical ordinal	Grades (Efron)	Direct observation with slit lamp, evaluated with Efron's scale	0	BV, V1 and FV	Pearson's χ^2 or Fisher's exact test. McNemar's test*
Chemosis	Categorical nominal	Present/absent	Observation	Absent	BV, V1 and FV	Pearson's χ^2 or Fisher's exact test. McNemar's test*
Primary outcome of safety						
AE	Quantitative discrete	Number of Cases (N)	Count	0	BV, V1 and FV	ANOVA
AE(bis)	Categorical nominal	Present/absent (-)	Observation	Absent	BV, V1 and FV	Pearson's χ^2 or Fisher's exact test.
BCVA	Quantitative discrete	Fraction (-)	Snellen chart	1	BV, V1 and FV	ANOVA Student's t test*
IOP	Quantitative discrete	Number	Tonometry	≥ 10 and ≤ 21	V1 and FV	ANOVA Student's t test*

OSDI, ocular surface disease index; TFRT, tear film rupture time; AEs, adverse events; BCVA, better corrected visual acuity; IOP, intraocular pressure; ANOVA, Analysis of Variance; χ^2, Chi-square. *When applicable.
						

Table 3. Operational definition of variables

The variables, method, and scales for their measurement are described in detail below. They are in order according to Table 3.

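### The printed non-inferiority hypothesis concerns a difference in proportions, but the tests named for OSDI test zero difference in means, and no rule compares a confidence limit with the margin

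*Combined protocol and SAP*

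**What the plan says.** Non-inferiority appears in three places.

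- Synopsis, Statistical methodology: "A 95% CI will be considered for the non-inferiority criteria based on the objectives of the study".
- Section 10.1.2: "A 95% confidence interval (95% CI) will be considered for non-inferiority criteria [60".
- Section 10.2.2, where the sample size uses "a non-inferiority margin (δ) of 10%, based on the following working hypotheses". The hypotheses that follow, also printed in the Synopsis, are H0: P_A − P_B ≤ δ and H1: P_A − P_B > δ.

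The tests named for comparing groups on the primary outcome, the OSDI score at day 31, are different in kind.

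- The Synopsis analyses "by means of the Analysis of Variance Test (ANOVA) for the quantitative variables for the difference between the groups".
- Table 3 in section 7.4.5 lists, for OSDI, "ANOVA Student's t test" (the t-test when applicable).
- Section 10.1.2 adds: "For equal variances, Tukey's post-hoc test will be used, otherwise Dunnett's statistic will be used". Significance is set at alpha 0.05 or less.

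The verbal hypothesis in section 3.4 concerns a 20% fall in OSDI in at least one dosage. Section 4.2 gives the purpose of the study, "which is to evaluate efficacy and ideal dosage". Sections 3.1 to 3.3 name no reference dosage.

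**The concern.** A non-inferiority conclusion needs a confidence limit for a stated difference to lie on the right side of a stated margin. ANOVA, Tukey, Dunnett and the t-test, used as significance tests, ask whether the difference is zero. Someone following section 10.1.2 would obtain p-values for a difference in means. For the non-inferiority criterion they would have an interval that is to be considered, with no instruction on which arms, which scale, which limit or what follows.

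All three arms receive the same product, so the comparison between dosages is the only randomised evidence on the ideal dosage. A non-significant comparison is a plausible result, and the plan has no rule for interpreting it. A rule chosen after the data are seen would be post hoc.

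**Working it through.** **1. Hypothesis and tests side by side**

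| Element | Printed hypothesis (Synopsis, 10.2.2) | Named OSDI analysis (Synopsis, Table 3, 10.1.2) |
|---|---|---|
| Parameter | difference in proportions | difference in means |
| Null value | margin of 10% | zero |
| Arms | two groups, A and B, not identified | three dosages |
| Decision | none beyond considering a 95% CI | p ≤ 0.05 |

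The two columns do not meet. No sentence carries the 10% margin onto the OSDI score.

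**2. The plan's own figure**

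Formula in 10.2.2 with k = 1: n = [P_A(1−P_A) + P_B(1−P_B)] × ((z_{1−α} + z_{1−β}) / (P_A − P_B − δ))². Stated inputs: one-sided α 0.05 (z = 1.645, as the formula is printed), power 80% (z = 0.842), δ 10%, and a 20% fall, taken as P_A = 0.20. P_B is not stated. With P_B = 0.10 and δ = −0.10:

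n = (0.16 + 0.09) × (2.4865 / 0.20)² = 38.64, so 39, and 39 × 1.2 = 46.8, so 47.

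The stated 39 and 47 are reproduced, but only with an unstated P_B and a negative margin. With equal arms at 0.20 the same formula gives 0.32 × (2.4865 / 0.10)² = 197.8, so 198 per group.

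**3. A 10-point deficit on the plan's proportion scale**

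Take 0.20 (the assumed fall) against 0.10 (0.20 less the margin), with a two-sided 0.05 test of no difference.

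- n = 39: SE under the null √(2 × 0.15 × 0.85 / 39) = 0.0809; SE under the alternative √(0.25 / 39) = 0.0801. Power ≈ Φ((0.10 − 1.96 × 0.0809) / 0.0801) = Φ(−0.73) ≈ 23%, so non-significant in about 77%.
- n = 47: SEs 0.0737 and 0.0729. Power ≈ Φ(−0.61) ≈ 27%, so non-significant in about 73%.

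Summing exact binomial probabilities for Pearson's chi-square gives 76% and 71%. The range is therefore 71–77%.

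**4. A deficit on the OSDI point scale**

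The documents give no SD, so SD is an assumption here, as is reading 10% as a fraction of baseline. Eligibility is OSDI 13 to 32. The midpoint 22.5 gives 2.25 points and the top gives 3.2. One dosage is worse by d and the other two are equal. ANOVA noncentrality is n × (2/3) × d² / SD²; for n = 39, d = 2.25 and SD 10 it is 39 × 0.667 × 5.0625 / 100 = 1.32. Probability of a non-significant result at n = 39:

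| d | SD (assumed) | ANOVA | Tukey, that pair | t-test |
|---|---|---|---|---|
| 2.25 | 10 | 84% | 91% | 84% |
| 2.25 | 8 | 77% | 87% | 77% |
| 2.25 | 5 | 49% | 65% | 50% |
| 3.2 | 5 | 17% | 33% | 20% |

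If 10% means ten points of percent change, Tukey misses it more than half the time only when the SD exceeds about 18.6 (n = 39) or 20.5 (n = 47) percentage points.

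**5. What a limit-against-margin rule would do**

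With a two-sided 95% CI, a dosage whose true deficit equals the margin passes 2.5% of the time, whatever the SD. For truly equal dosages with n = 39, SD 10 and a 2.25-point margin, SE = 10 × √(2/39) = 2.265, and the pass rate ≈ Φ(2.25 / 2.265 − 1.96) = Φ(−0.97) ≈ 17%. The t distribution gives about 16%.

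**The case against.** The strongest reply is that the plan does not commit the error a reader might infer. A reader might conclude that p > 0.05 will be reported as non-inferiority, so that a margin-sized deficit would usually pass unnoticed. No sentence says so. Section 10.1.2 puts the significance level and the 95% CI for non-inferiority in separate sentences, which suggests that an interval method was intended. That stands.

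Four further replies have force.

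- The printed hypotheses do name a parameter and a direction, so it is wrong to say that nothing is specified.
- Tukey and t procedures can supply intervals for pairwise differences. What is missing is the comparison with a margin.
- The documents never say that the non-inferiority comparison is between dosages. That is inferred from the dosages being the only arms. Section 6.1.2.1 expects four times a day to be optimal, but does not make it a reference.
- Significance is not the only criterion written for OSDI; section 3.4 also has the 20% fall.

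The word *usually* fails as a general statement. On the OSDI scale it depends on the assumed SD and on how the 10% is read, and step 4 includes a case with only 17% missed.

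None of this supplies the missing link. The parameter printed is not the one analysed, and the plan never states which limit must clear which margin.

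**Conclusion.** The concern holds in this form: the tests named for OSDI do not address the printed non-inferiority hypothesis, because they test zero difference in means, while the hypothesis is a margin on a difference in proportions between two unidentified groups. This part rests on the text alone.

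The documents do not support saying that the sponsor will treat non-significance as non-inferiority. They support a narrower statement: a non-significant result could not bear that reading. With 39–47 per group, a 10-point deficit on the proportion scale is non-significant in about 71–77% of trials, taking 0.20 against 0.10. On the OSDI point scale the ANOVA rate at n = 39 runs from 17% to 84% over the cases shown, and it rests on assumed SDs.

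This should be fixed, but it is not a fatal flaw: no stated objective claims non-inferiority. It needs to be reconciled with the hypothesis and margin statements in the Synopsis, 3.4 and 10.2.2, although correcting those alone would still leave 10.1.2 without a decision rule.

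**What to change.** Choose one of two routes and apply it consistently in the Synopsis, 10.1.2 and 10.2.2.

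(a) **Drop non-inferiority.** Delete the wording in the Synopsis and 10.1.2, and in 10.2.2 stop describing the sample size as powered for non-inferiority. Report pairwise differences in day-31 OSDI with multiplicity-adjusted 95% CIs, and state that a non-significant difference is not evidence that dosages are similar.

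(b) **Keep it and make it testable.** Name the reference arm in advance and state and justify the margin in the units analysed. Higher OSDI is worse, so declare non-inferiority only if the upper limit of the two-sided 95% CI for dosage minus reference lies below the margin. Restate the power on that scale, with the assumed SD and its source.

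Route (a) costs a few sentences and a new rationale for the sample size, with no new data. Route (b) needs a new margin and probably a new sample size: with 39 per arm, an assumed SD of 10 and a 2.25-point margin, truly equal dosages would pass only about 16% of the time. Unless the sponsor can support a much smaller SD or a wider margin, that favours (a).

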3.2 Specific objective

- To assess the safety of 3 doses of Multi-dose Lagricel® Ofteno in patients with mild to moderate dry eye by means of the incidence of unexpected AEs related to the investigational product.

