6.1 Administered product

1. Investigational product

- Generic name: Sodium hyaluronate.
- Distinctive name: Multi-doses Lagricel® Ofteno.
- Active ingredients: Sodium hyaluronate 0.4%.

- 
- Pharmaceutical form: Ophthalmic solution.
 - Presentation: Multi-dose dropper bottle.
 - Prepared by: Laboratorios Sophia, S.A. de C.V.
 - Solution Description: Transparent solution, free of visible particles.
 - Packaging description: White bottle with a capacity of 10 mL, made of low-density polyethylene.

2. Dose of the investigational medicinal product

Three different dosages will be used, each of the groups will use one of the following:

- One drop BID, OU, for 30 days (suggested time between applications is 12 hours).
- One drop QID, OU, for 30 days (minimum time between applications of 3 hours).
- One drop 6x/D, OU, for 30 days (minimum time between applications of 3 hours).

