7.4.2 Primary outcome of safety

- Incidence of AEs (ET: days 15 and 31).

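### The only planned inference on adverse-event incidence is a difference test between three arms that all receive the product, so it cannot address the safety of each dosage; AE incidence should be estimated with confidence intervals.

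*Combined protocol and SAP*

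**What the plan says.** The specific objective (3.2) is "To assess the safety of 3 doses of Multi-dose Lagricel® Ofteno in patients with mild to moderate dry eye", to be judged by the incidence of unexpected AEs related to the product. The primary safety outcome (7.4.2) is AE incidence at days 15 and 31. On the arms, 6.1 states "Three different dosages will be used, each of the groups will use one of the following": BID, QID or 6x/D of the same solution. There is no vehicle, untreated or active-control arm.

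Table 3 (7.4.5) assigns ANOVA to the AE count and Pearson chi-square or Fisher's exact test to AE present/absent. Most other rows also list a paired test; the AE rows do not. Section 10.1.2 adds:

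- on table layout: "The statistical analysis to identify significant differences in the qualitative variables will be carried out by creating 2x2 contingency tables"
- on the comparison of dosages: "Difference between groups: Pearson's Chi-square test (X^2) or Fisher's exact test at expected values less than 5"
- on how categorical results, AEs among them, are shown: "The result of the nominal and ordinal qualitative variables will be presented in frequencies, proportions and percentages"
- on the threshold used throughout: "The level of difference to consider significance will be an alpha (α) of 0.05 or less"

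The one confidence interval in that section reads "A 95% confidence interval (95% CI) will be considered for non-inferiority criteria [60". The only margin in the document, 10%, belongs to the sample-size calculation based on OSDI (10.2.2). No interval, precision or acceptable rate is attached to AE incidence.

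**The concern.** The objective asks an absolute question about each dosage: how often do subjects have AEs, and how high could the true rate plausibly be? The test asks a relative one: do the dosages differ? With every arm exposed to the same product, an effect common to all arms cancels out of the comparison. That case is realistic, because 7.4.5.7 lists AEs expected from the drop itself, such as burning, irritation and blurred vision.

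The test could still help if it reliably detected a rise in AEs with more frequent dosing, which matters for a trial meant to identify the best dosage. The sample size was not set for that purpose. A non-significant result would therefore be the likely outcome if the product were harmless, if it were equally troublesome at all three frequencies, or if it were moderately worse at the highest one. The report would have a p-value that does not separate these cases, and percentages without a measure of uncertainty.

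**Working it through.** **Inputs.** 47 per arm, 141 in total (10.2.1); two-sided difference tests at alpha 0.05 with Fisher when an expected count is below 5 (10.1.2); safety set of all subjects exposed at least once (10.1.3). AE rates are my assumption, since the documents give none.

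**The plan's own figure.** 39 × 1.2 = 46.8, rounded to 47, and 3 × 47 = 141. This is an efficacy calculation. There is no stated power or precision for AEs to reproduce.

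**Step 1: the same AE rate in every arm.** Chance of a non-significant result, 47 per arm. The three-arm figures are simulated; the pairwise figures are exact binomial enumeration under the plan's rule.

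| Common AE rate | Three-arm chi-square | One pairwise test |
|---|---|---|
| 5% | 96% | 99% |
| 20% | 95% | 95% |
| 30% | 95% | 95% |
| 50% | 95% | 95% |

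The result hardly depends on the rate. A test of equality has its nominal error rate, or less, whenever the arms are equal.

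**Step 2: AE rates that differ between two dosages.** Worked example, 10% v 20%, normal approximation:

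- pooled rate 0.15; null SE = √(2 × 0.15 × 0.85 / 47) = 0.0737
- SE under the alternative = √((0.10 × 0.90 + 0.20 × 0.80) / 47) = 0.0729
- power = Φ((0.10 − 1.96 × 0.0737) / 0.0729) = Φ(−0.61) = 0.27, so about 73% missed

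Exact enumeration under the plan's chi-square/Fisher rule gives:

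| Assumed rates | Missed |
|---|---|
| 5 v 10% | 92% |
| 10 v 20% | 72% |
| 10 v 25% | 50% |
| 10 v 30% | 30% |
| 5 v 25% | 18% |

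**Step 3: three-arm test.** Simulated misses: 10/15/20%, 80%; 5/10/15%, 73%; 10/20/30%, 42%; 10/10/30%, 25%. The range over the patterns tried, each with a spread of 10 to 20 points, is 25–80%. Section 10.1.2 speaks of 2x2 tables, so the pairwise figures in Step 2 follow the text more closely. Three uncorrected pairwise tests would also carry a false-positive risk of up to 1 − 0.95³ = 14% if they were independent.

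**Step 4: what estimation gives at the same size.** Exact (Clopper-Pearson) two-sided 95% intervals:

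- 0 of 47: upper limit 1 − 0.025^(1/47) = 7.5%
- 5 of 47 (10.6%): 3.5% to 23.1%
- 0 of 141 pooled: upper limit 1 − 0.025^(1/141) = 2.6%

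For a difference between two arms with a common rate p, the 95% half-width is 1.96 × √(2p(1−p)/47): about 9, 12 and 16 points at p = 5%, 10% and 20%. These intervals are wide, but they tell the reader which rates and differences the trial has not excluded.

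**The case against.** The fairest defence is that the p-value is not the whole safety assessment. Frequencies and percentages are to be reported, and AEs by number of subjects, so a common rate of 30% or 50% would be plain in the tables. AEs are graded for seriousness, severity and causality (8.1.2, 8.1.7). Sections 7.4.5.1 to 7.4.5.9 set AE triggers for individual subjects that need no comparison arm, such as IOP of 22 mm Hg or more, or any chemosis. Section 11.3 contemplates suspension or termination if serious AEs exceed 10% of a group. The sample size was never meant for safety, and unpowered AE tests beside descriptive tables do not invalidate a phase II plan.

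All of that stands, and it limits the point. It does not remove it. The triggers define what counts as an AE in one subject; they do not say how the incidence is to be judged. The 10% threshold concerns stopping and serious AEs only, and is not a criterion for overall AE incidence. The percentages carry no interval, and in groups of 47 the uncertainty is large: five affected subjects are compatible with a true rate anywhere from 3.5% to 23.1%.

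**Conclusion.** The point holds as a mismatch between objective and method. The only inference planned for the primary safety outcome cannot address the safety of each dosage, and it has limited ability to detect a rise in AEs with frequency. The first part needs no assumed rate: about 95% or more of results are non-significant at every common rate tried. The second part rests on assumed AE rates and 47 per arm, with pairwise misses from 18% to 92% in the scenarios shown. It should be quoted as a range.

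Three stronger readings are tempting and not supported:

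- **That the plan will declare safety from p > 0.05.** No section says so, and the formal hypotheses (3.4) concern OSDI only. The gap is that no other basis for inference is specified.
- **That a fixed share of relevant differences would be missed.** The documents define neither an expected AE rate nor a relevant difference.
- **That BCVA and IOP have the same defect.** Table 3 lists Student's t test for both where applicable, 10.1.2 plans intragroup analysis, and the outcomes are changes. A within-group change can reveal an effect common to all arms.

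The improvement is cheap and should be made before analysis.

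**What to change.** Amend 10.1.2 and the AE rows of Table 3 so that the primary safety analysis is one of estimation:

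1. For each dosage and pooled over the three, report the number and percentage of subjects with (a) at least one AE, (b) at least one product-related AE and (c) at least one unexpected product-related AE, the measure named in 3.2. Give exact two-sided 95% confidence intervals.
2. Report risk differences for QID and 6x/D versus BID with 95% confidence intervals.
3. Keep chi-square/Fisher as descriptive only, and state that p > 0.05 will not be reported as evidence that the dosages are safe or equally safe.
4. For BCVA and IOP, add 95% confidence intervals for mean change to the within-group tests already planned.

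The cost is SAP wording and a few table columns, with no new subjects, visits or data. The downside for the sponsor is that a finding of no significant difference can no longer serve as a safety result, and the intervals will be wide enough to show how much remains unknown.
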